5.7 Duration of Therapy

If at any time the constraints of this protocol are considered to be detrimental to the patient's health and/or the patient no longer wishes to continue protocol therapy, the protocol therapy should be discontinued and the reason(s) for discontinuation documented in the case report forms.

Patients will be removed from the study for any of the following reasons:

- Disease progression or relapse
- Death
- Adverse event(s) that, in the judgment of the investigator, may cause severe or permanent harm or which rule out continuation of study drug
- General or specific changes in the patient's condition render the patient unacceptable for further treatment in the judgment of the investigator
- Suspected pregnancy
- Serious noncompliance with the study protocol
- Lost to follow-up
- Patient withdraws consent
- Investigator removes the patient from study
- The Siteman Cancer Center decides to close the study

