8.0 STUDY CALENDAR

Please note that all assessments allow a window of +/-3 days for scheduling issues.

	Screening		Consolidation ³			Restaging ⁴	Maintenance ⁵			EOS ⁷	F/U ⁸
	Prior to ASCT ¹	Prior to beginning consolidation ²	D1	D8	D15		D1	D8	D15		
Informed consent	X										
H&P, ECOG PS, plasmacytoma assessment	X	X	X ¹³			X	X ^{13,14}			X	X ¹⁵
CBC & CMP	X		X ¹³		X ⁶	X	X ^{13,14}			X	
SPEP and immunofixation	X	X	X ¹³			X	X ^{13,14}			X	
24h urine for total protein, UPEP, and immunofixation ⁹	X	X	X ¹³			X	X ^{13,14}			X	
Serum-free light chains & β2 microglobulin	X	X	X ¹³			X	X ^{13,14}			X	
Quantitative immunoglobulins (IgA, IgG, IgM)	X	X	X ¹³			X	X ^{13,14}			X	
Serum βhCG ¹⁰	X	X	X				X			X	
Bone marrow biopsy and aspirate ¹¹	X	X				X	X ¹⁶				
Central labs ¹² (MRD Analysis)		X				X	X ¹⁶				
Central labs ¹² (Hevylite)	X		X ¹³			X	X ^{13,14}			X	
Central labs ¹⁸ (Sub-study)		X ¹⁸					X ¹⁸				
Ixazomib			X	X	X		X	X	X		
Lenalidomide			Days 1-21				Days 1-28				
Dexamethasone			X	X	X						
Administration Questionnaire ¹⁷			X				X				
Adverse events assessment			X ----- X								

1. Day -60 to Day -2

2. Day +80 to Day +120; to occur within 28 days prior to C1D1 of consolidation

3. 4 28-day cycles

4. Prior to beginning maintenance (approx. Day +192 to Day +232); to occur within 28 days after completing C4 of consolidation and within 28 days prior to C1D1 of maintenance

5. 28-day cycles; continued until progression or unacceptable toxicity

6. Cycles 1-2 only

7. Within 30 days of last dose of study drug(s)

8. Every 3 months for 18 months

9. Repeat 24h urine only required for patients with ≥ 200 mg/24h of M-protein at screening

10. Women of childbearing potential only; 2 negative tests are required within 14 days before study drug dosing on C1D1 of consolidation

11. Bone marrow aspirate and core biopsy – differential required; Cytogenetics, and fluorescent *in situ* hybridization (FISH) studies performed per institutional guidelines.

12. See Section 9.0

13. Not required on C1D1 if screening/restaging visit occurred within 28 days prior

14. C1-C4 then every 3 cycles thereafter (i.e., C7, C10, C13 ...)

15. A telephone call to assess OS and PFS can be made in lieu of a physical exam

16. Cycle 13 for all patients. Cycle 25 and 37 also required for patients in suspected or confirmed CR/sCR at that time.

17. See Appendix D. Patient to complete following each cycle of study treatment (consolidation and maintenance).

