12.1.6 Progressive Disease or Clinical Relapse

Progressive disease (PD) requires one or more of the following:

- $\geq 25\%$ increase in the level of serum monoclonal protein, which must also be an absolute increase of at least 0.5 g/dL and confirmed on a repeat investigation
- $\geq 25\%$ increase in 24-hour urine monoclonal protein, which must also be an absolute increase of at least 200 mg/24hr and confirmed on a repeat investigation.
- If serum and urine monoclonal protein are unmeasurable, $\geq 25\%$ increase in the difference between involved and uninvolved free light chain levels, which must also be an absolute increase of at least 10 mg/dL and confirmed on a repeat investigation
- $\geq 25\%$ increase in plasma cells in a bone marrow aspirate or on trephine biopsy, which must also be an absolute increase of at least 10%.
- Definite increase in the size of existing lytic bone lesions or soft tissue plasmacytomas. A definite increase is defined as at least 50% (and at least 1 cm) increase as measured serially as the sum of the products of the cross-diameters of the lesions.
- Development of new bone lesions or soft tissue plasmacytomas (not including compression fracture).
- Development of hypercalcaemia (corrected serum calcium > 11.5 mg/dL or 2.8 mmol/L not attributable to any cause other than progressive multiple myeloma).
- Decrease in hemoglobin > 2 g/dl not attributable to any cause other than progressive multiple myeloma
- Increase in creatinine by > 2 mg/dl not attributable to any cause other than progressive multiple myeloma
- Other worsening laboratory result, or clinical condition that the treating physician determines is not attributable to any cause other than progressive multiple myeloma

Note: A response of progressive disease/clinical relapse nullifies any other concurrent response. For example, at a given time point a participant meets criteria for VGPR but has development of new bone lesions the response is PD not VGPR.

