15.3 Data Analysis

For the analysis of consolidation therapy, the data for safety analysis will include these patients who have at least 1 dose of IRD consolidation therapy, while the data for efficacy analysis will include patients who complete 4 cycles therapy. Demographic and clinical characteristics of the sample, as well as adverse events, complications and loss to follow-up will be summarized using descriptive statistics. The change of MRD-negative rates for pre- and post-consolidation therapy will be described using contingency table and compared by McNemar test. The incidences of mortality, progression, relapse, as well as tumor response (complete response and overall) and their 95% confidence intervals following consolidation therapy will also be calculated.

Data analysis for maintenance portion will be performed following the intent-to-treat (ITT) principle. The balance of demographic and baseline clinical characteristics between two arms will be compared using t-test, Mann-Whitney rank-sum test, or Chi-square test as appropriate. The distributions of responses and adverse events across two arms will be summarized using contingency tables and compared by 2-sample Chi-square test or Fisher's exact test. Contingency table and Fisher's exact test will also be used to assess the between-arms difference for the rates of conversion from MRD-positive to MRD-negative. Chi-square test will be used to compare the distribution of responses, and Kaplan-Meier curves with log rank tests will be used to compare PFS and OS.

Overall survival (OS) will be defined as time from ASCT to death due to any causes, and survivors will be censored at withdrawal or study closeout. Progression-free survival (PFS) will be defined as time from ASCT to progression, relapse, or death, whichever occurs first, and those event-free survivors will be censored at withdrawal or study closeout. The between-arm differences in OS and PFS will be described using Kaplan-Meier product limit estimator and compared by log-rank tests. Kaplan-Meier curves will also be used to describe the association between MRD status (both prior to and after consolidation therapy) and OS or PFS, and proportional hazards Cox models will be used to control the potential confounding effects of other patient and clinical characteristics.

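### Patients who leave protocol therapy without progression have no scheduled myeloma labs and no contact after 18 months, yet may be counted as progression-free to closeout

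*Combined protocol and SAP*

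**What the plan says.** - **Labs.** In the Section 8.0 calendar the row "SPEP and immunofixation" and the rows for 24-hour urine, free light chains, immunoglobulins and blood counts/chemistry have their last mark at the end-of-study visit, due within 30 days of the last dose. During maintenance the myeloma labs run "C1-C4 then every 3 cycles thereafter", about every 12 weeks.
- **Follow-up.** The follow-up column has one mark, for history, examination and plasmacytoma assessment, timed "Every 3 months for 18 months". Its note reads: "A telephone call to assess OS and PFS can be made in lieu of a physical exam". Section 5.8 ends follow-up 18 months after removal. The Protocol Summary expects about 7 years of participation per patient.
- **Data forms.** Section 10.0 asks for the myeloma lab form at baseline and at each treatment cycle, with no follow-up submission.
- **Progression.** Under Section 12.1.6 a serum M-protein event needs a rise of at least 25%, "which must also be an absolute increase of at least 0.5 g/dL and confirmed on a repeat investigation". The urine and light-chain routes are similar. Relapse from CR (12.1.7) rests largely on immunofixation, electrophoresis or marrow.
- **Reasons for removal.** Section 5.7 lists progression, "Adverse event(s) that, in the judgment of the investigator, may cause severe or permanent harm or which rule out continuation of study drug", and withdrawal of consent as separate items.
- **Censoring.** Section 15.3 analyses maintenance by intention to treat. For PFS, "those event-free survivors will be censored at withdrawal or study closeout". Withdrawal is not defined, and no rule refers to the last disease assessment.

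**The concern.** On treatment, progression is sought with scheduled M-protein measurements. After a stop without progression, the same endpoint rests on an examination or a call, and after 18 months on nothing. If such a patient is carried event-free to closeout, a progression that nobody looked for becomes progression-free time.

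Stops without progression need not be equally common in the two maintenance arms. The arm with more of them would be observed less and could look better on PFS. The PFS hazard ratio is read against 1.3 in the non-inferiority illustration (15.1) and in the futility rule (15.4). More stops on ixazomib would make non-inferiority too easy to claim. More stops on lenalidomide would make it too hard, and would push the ratio towards the futility line. The PFS estimate for consolidation is exposed in the same way, but only for patients who leave protocol therapy altogether.

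**Working it through.** **Inputs from the documents.** 5-year event rate on lenalidomide about 54%, 110 patients per arm, margin of 10 points or HR 1.3, one-sided 90% confidence limit (15.1); 18 months of follow-up after removal (5.8); about 7 years of participation (Protocol Summary).

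**Assumptions, because the documents give no figure.** Stop rates without progression by 24 months, the share of off-treatment progressions never recorded, constant hazards, closeout 60 to 96 months after the start, stopping unrelated to prognosis, and no crossover.

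**1. The plan's own figures.** The hazard is λ = −ln(0.46)/60 = 0.01294 per month. HR 1.3 gives 1 − 0.46^1.3 = 0.636, or 9.6 points above 54%, which matches the 10-point margin. Repeating the plan's binomial simulation gives power of 78.7% when ixazomib is truly 4 points better and 82.8% when it is 5 points better. The stated 80% is reproduced.

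**2. Unobserved time for one patient.** A patient who stops at month 12 has the last contact at month 12 + 18 = 30. With closeout at month 84, closeout censoring credits 84 − 30 = 54 months without any contact.

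**3. Events at risk of being missed.** With a stop rate s by 24 months, the stop hazard is σ = −ln(1 − s)/24. The probability of an event by 5 years that falls after stopping is 0.54 − [λ/(λ+σ)] × [1 − exp(−60(λ+σ))].
- s = 20%: σ = 0.00930, so 0.54 − 0.582 × 0.737 = 0.111.
- s = 10%: σ = 0.00439, so 0.54 − 0.747 × 0.647 = 0.057.

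If half are missed, a true 54% reads 0.54 − 0.056 = 48.4% in the first arm and 0.54 − 0.029 = 51.1% in the second, although the arms are equal. With equal stops of 10% in both arms, both read about 51% (half missed) to 48% (all missed), and the hazard ratio does not move.

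**4. Hazard ratio when the arms are truly equal** (simulation; arm with more stops over arm with fewer; 30% to 80% of off-treatment progressions missed; runs agree to about 0.01)

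| Censoring of event-free patients | 20% v 10% stops | 30% v 15% stops |
|---|---|---|
| At closeout | 0.95 to 0.87 | 0.93 to 0.81 |
| At the end of the 18-month follow-up | 0.98 to 0.94 | 0.97 to 0.91 |
| At the stop itself | 1.00 | 1.00 |

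If progressions are found 6 to 12 months late instead of being lost (30% v 15% stops, closeout censoring, 60–80% affected), the ratio is about 1.00 to 0.95.

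**5. Effect on the non-inferiority reading** (plan's 5-year rates and one-sided 90% limit; stops 20% v 10%; half missed; closeout censoring)
- *More stops on ixazomib, true HR 1.30.* The rates read about 57.3% v 51.0% instead of 63.6% v 54%. The chance of claiming non-inferiority rises from 10.6% to 23%.
- *More stops on lenalidomide, true HR 1.00.* The rates read about 51.3% v 48.2%. The chance of claiming non-inferiority falls from 58% to 40%.
- *Extreme case.* With 30% stops on lenalidomide v 10% on ixazomib and every off-treatment progression missed, a true HR of 1.00 reads about 1.35, past the futility line.

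**The case against.** A reader might infer that everyone who stops for toxicity is lost to PFS, that only symptomatic progression can surface, and that PFS is therefore overstated by a known amount. The documents do not support that.

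- **Many who stop stay on the lab schedule.** Sections 5.3.2 and 5.3.3 allow crossover with the Principal Investigator's permission, with full protocol follow-up. Section 5.1 directs patients who stop one drug for toxicity during consolidation preferentially to the opposing arm. If half of those who stop cross over (an assumption), and the rest are censored when the 18-month follow-up ends, the ratio is about 0.99 to 0.97.
- **Local results can still be reported.** The 3-monthly contact is meant to assess PFS, and nothing forbids recording a progression found on local blood tests. Section 12.1.6 also accepts other laboratory or clinical worsening judged by the treating physician. Late detection may be nearer the truth than permanent loss.
- **Withdrawal could mean removal from treatment.** Patients would then be censored at the stop, without bias if stopping is unrelated to prognosis.
- **Later deaths count.** PFS includes death, so some missed progressions become late events, which the simulation ignores.
- **The comparison is a pilot.** PFS is secondary, and Section 15.1 says the study was not powered for non-inferiority or superiority.

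All of this stands as a limit on size and severity, but it does not close the gap. Crossover needs permission and will not cover everyone. Local results have no scheduled form. Because Section 5.7 lists withdrawal of consent separately, and calls to assess PFS would serve little purpose if patients were already censored at the stop, the consent reading is the more natural one. On the other reading, censoring may be informative, so the term needs defining either way.

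**Conclusion.** The point holds for patients who leave protocol therapy without progression and neither cross over nor move to the opposing arm. They have no scheduled myeloma labs after the end-of-study visit and no contact after 18 months. Read as consent withdrawal, the censoring rule credits them with event-free time that was not observed. PFS may be overstated, more in the arm with more such stops.

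The bias runs from near nil to moderate: a true hazard ratio of 1.00 reads about 0.95 to 0.81 under closeout censoring, 0.98 to 0.91 if censored when contact ends, and 1.00 to 0.95 if progressions are only found late. It is smaller still with crossover. These figures rest on assumed stop rates and missed shares.

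The documents do not show which arm would benefit, so a reader should not infer that the plan favours ixazomib. The value of 1.35 comes from an extreme case and is no forecast of a futility stop. The primary MRD comparison, before and after consolidation, is unaffected. For a secondary, pilot endpoint that still feeds the 1.3 futility rule, this should be fixed, but it does not undermine the trial.

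**What to change.** 1. **Section 15.3.** Define withdrawal. Censor PFS for event-free patients at the last adequate disease assessment, and state what makes an assessment adequate. Add a sensitivity analysis for patients off treatment.
2. **Section 8.0 and the data form schedule in Section 10.0.** For patients removed without progression, record locally obtained SPEP/immunofixation and free light chain results, with urine where applicable, at the existing 3-monthly follow-up contacts until progression or next anti-myeloma therapy.
3. **Telephone note in Section 8.0.** A call without such results should not count as an adequate PFS assessment. It can still serve for survival.

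The first change alone removes the unobserved time but may leave informative censoring if stopping is related to prognosis, which is why the local results are needed too. The cost is an amendment, some extra data abstraction and earlier censoring of some patients. No additional marrow sampling is needed.

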9.0 CENTRAL LABS

9.1 Mayo Clinic MFC MRD Panel

Approximately 5 ml of bone marrow aspirate in EDTA (pink top) tube(s) will be collected at the following time points:

- Prior to beginning consolidation therapy
- Prior to beginning maintenance therapy
- Cycle 13 Day 1 of maintenance therapy
- Cycle 25 Day 1 of maintenance therapy*
- Cycle 37 Day 1 of maintenance therapy*

*- Only required for patients in suspected or confirmed CR/sCR at that time

9.2 Adaptive ClonoSEQ MRD Testing

If archived bone marrow aspirate or core slides or sections are available from the time of diagnosis or any time prior to study entry, they will be requested.

Additionally, approximately 5 ml of bone marrow aspirate in EDTA (pink top) tube(s) will be collected at the following time points:

- Prior to beginning consolidation therapy
- Prior to beginning maintenance therapy
- Cycle 13 Day 1 of maintenance therapy
- Cycle 25 Day 1 of maintenance therapy*
- Cycle 37 Day 1 of maintenance therapy*

*- Only required for patients in suspected or confirmed CR/sCR at that time

9.3 HEVYLITE Assay

Approximately 10 ml of peripheral blood in serum (red top) tube(s) will be collected at the following time points:

- Prior to ASCT
- Prior to beginning consolidation therapy
- Day 1 of each cycle of consolidation therapy
- Prior to beginning maintenance therapy
- Day 1 C1-C4 of maintenance and then every 3 cycles thereafter
- End of Study

9.4 Handling of Specimen(s)

Instructions for handling and shipment of central labs will be provided in the study lab binder.

9.5 Future Research

Any remaining specimens from blood or marrow after the required correlative studies are completed will be stored for future research including, but not limited to, genetic studies.

10.0 DATA SUBMISSION SCHEDULE

Case report forms with appropriate source documentation will be completed according to the schedule listed in this section. Electronic data management systems will be used in this trial in collaboration with the Division of Biostatistics at Washington University.

REDCap is a web-based clinical studies data management system that will be used for capture of clinical data from this trial. The case report forms developed for this trial will be transformed to electronic format. An electronic study calendar will drive the study's data collection workflow.

Each participating center has access only to data from its own participants. Washington University, as the data coordinating center, has access to data from all sites. Training in entering data in REDCap is required before a participating center will be given access to the database. In addition, a participating center must have IRB approval of this protocol prior to initiation of REDCap data entry training, which must be completed prior to site study activation.

Case Report Form	Submission Schedule
Original Consent Form	Prior to registration
Registration Form Eligibility Form Medical History Form Treatment History Form Safety Labs Form MM labs Form Stem Cell Transplant Form	At Baseline
Study Drug Dosing Form Safety Labs Form MM Labs Form Response Form	Each Cycle of Treatment
Bone Marrow Form Response Form	As Per Protocol Requirements
Correlative Studies Form	As Per Protocol Requirements
Adverse Events	Continuous from baseline through safety follow-up visit
MedWatch Form	See Section 8.0 for reporting requirements

Any queries generated by Washington University must be responded to within 28 days of receipt by the participating site. The Washington University research team will conduct a regular review of data status at all secondary sites, with appropriate corrective action to be requested as needed.

11.0 REGULATORY AND REPORTING REQUIREMENTS

The entities providing oversight of safety and compliance with the protocol require reporting as outlined below.

The Washington University Human Research Protection Office (HRPO) requires that all events meeting the definition of unanticipated problem or serious noncompliance be reported as outlined in Section 11.4.

The FDA requires that all serious and unexpected adverse events be reported as outlined in Section 11.7. In addition, any fatal or life-threatening adverse experiences where there is a reasonable possibility of relationship to study intervention must be reported.

11.1 Definitions

11.1.1 Adverse Events (AEs)

Definition: any unfavorable medical occurrence in a human subject including any abnormal sign, symptom, or disease.

Grading: the descriptions and grading scales found in the revised NCI Common Terminology Criteria for Adverse Events (CTCAE) version 4.0 will be utilized for all toxicity reporting. A copy of the CTCAE version 4.0 can be downloaded from the CTEP website.

Attribution (relatedness), Expectedness, and Seriousness: the definitions for the terms listed that should be used are those provided by the Department of Health and Human Services' Office for Human Research Protections (OHRP). A copy of this guidance can be found on OHRP's website:

<http://www.hhs.gov/ohrp/policy/advevntguid.html>

11.1.2 Serious Adverse Event (SAE)

Definition: any adverse drug experience occurring at any dose that results in any of the following outcomes:

- Death
- A life-threatening adverse drug experience
- Inpatient hospitalization or prolongation of existing hospitalization
- A persistent or significant disability/incapacity (i.e., a substantial disruption of a person's ability to conduct normal life functions)
- A congenital anomaly/birth defect
- Any other experience which, based upon appropriate medical judgment, may jeopardize the subject and may require medical or surgical intervention to prevent one of the outcomes listed above

All unexpected SAEs must be reported to the FDA.

11.1.3 Unexpected Adverse Experience

Definition: any adverse drug experience, the specificity or severity of which is not consistent with the current investigator brochure (or risk information, if an IB is not required or available).

Events that are both serious AND unexpected must be reported to the FDA.

11.1.4 Life-Threatening Adverse Experience

Definition: any adverse drug experience that places the subject (in the view of the investigator) at immediate risk of death from the reaction as it occurred, i.e., it does not include a reaction that, had it occurred in a more severe form, might have caused death.

Life-threatening adverse experiences must be reported to the FDA.

